9.0 Confidentiality, Privacy and Data Management

For research being conducted at Penn State Hershey or by Penn State Hershey researchers only, the research data security and integrity plan is submitted using “HRP-598 – Research Data Plan Review Form Application Supplement”, which is available in the Library in CATS IRB (<http://irb.psu.edu>). Refer to Penn State College of Medicine IRB’s “Standard Operating Procedure Addendum: Security and Integrity of Human Research Data”, which is available on the IRB’s website. **In order to avoid redundancy, for this section state “See the Research Data Plan Review Form” in section 9.0 if you are conducting Penn State Hershey research and move on to section 10.**

For all other research, in the sections below, describe the steps that will be taken to secure the data during storage, use and transmission.

9.1 Confidentiality

9.1.1 Identifiers associated with data and/or specimens

List the identifiers that will be included or associated with the data and/or specimens in any way (e.g., names, addresses, telephone/fax numbers, email addresses, dates (date of birth, admission/discharge dates, etc.), medical record numbers, social security numbers, health plan beneficiary numbers, etc.).

If no identifiers will be included or associated with the data in any way, whether directly or indirectly, please indicate this instead.

The identifiers include code numbers “VRET001, VRET 002, ... VRET 00X, etc.” that will be linked with the participant’s name and email address in a password-protected master list code only accessible to the PIs and study team members of this project.

To maintain confidentiality of video tapes recorded of the clinical interviews and for each therapy session, these tapes will be labeled with participant code numbers and session numbers (e.g., VRET001-Session 1, VRET001-Session 2, ... VRET001-Session X). These tapes are also stored in a password protected, private, and secure PSU Box folder that is only available to the PIs and study team members of this project. This password protected server has a two-factor authentication feature for added security.

9.1.1.1 Use of Codes, Master List

If identifiers will be associated with the data and/or specimens (as indicated in section 9.1.1 above), describe whether a master record or list containing a code (i.e., code number, pseudonyms) will be used to separate the data collected from identifiable information, where that master code list will be stored, who will have access to the master code list, and when it will be destroyed.

If identifiers are included or associated with the data as described in section 9.1.1 above, but no master record or list containing a code will be used, it will be assumed by the IRB that the investigator plans to directly link the identifiers with the data.

The master code list will be stored in a secure and password protected server online using PSU Box at the [name] Lab, PSU University Park campus. Only [name], [name], and trained study team members will have access to the master code list and therapy video tapes. We plan to destroy the master code list that it is stored in a password protected and secure server that

minimizes the risk of breaching participants' confidentiality after 5 years of completing the research study.

9.1.2 Storage of Data and/or Specimens

Describe where, how and for how long the data (hardcopy (paper) and/or electronic data) and/or specimens will be stored. NOTE: Data can include paper files, data on the internet or websites, computer files, audio/video files, photographs, etc. and should be considered in the responses. Refer to the "Investigator Manual (HRP-103)" for information about how long research records must be stored following the completion of the research prior to completing this section. HRP-103 can be accessed by clicking the Library link in CATS IRB (<http://irb.psu.edu>).

Please review [Penn State's Data Categorization Project](#) for detailed information regarding the appropriate and allowable storage of research data collected according to [Penn State Policy AD71](#). Although the IRB can impose greater confidentiality/security requirements (particularly for sensitive data), the IRB cannot approve storage of research data in any way or using any service that is not permissible by [Penn State Policy AD71](#).

Paper data:

Physical consent forms and MINI clinical interviews will be kept in a locked room in the [name] Laboratory (either rooms 378, 380, 348A, 348B, 348C, or 381 Moore) for a maximum period of 5 years. These consent forms will be stored separately from the study data.

Video recordings:

We will use the computer webcams installed on the College of Liberal Arts computers in the Moore building to ensure treatment fidelity. Once these videos have been recorded, the research personnel will immediately upload it onto the encrypted, secure, and password protected PSU Box folder and the webcam version will be deleted. Videos stored in the safe and encrypted PSU Box folder will be destroyed 5 years after the close of the study. The videos will not be transcribed.

Online data:

Based on the policies of AD 95 (<https://policy.psu.edu/policies/ad95>) and AD 53 (<https://policy.psu.edu/policies/ad53>), we will use moderate security control. We are planning to store data on Qualtrics for a maximum period of 5 years after the close of the study. The Qualtrics website is highly secure. All surveys hosted with Qualtrics are encrypted using 256-bit SSL Technology (Secure Socket Layer) that is equivalent to the industry standard for securely transmitting credit card information over the Internet. This technology encrypts BOTH the questions displayed to the participants and their responses. Thus, all responses are instantly encrypted and remain so until they are received at the Qualtrics database. Interception of data when it is being transmitted between the Internet browser (i.e., Internet Explorer, FireFox, Safari, Chrome) and the Qualtrics database is HIGHLY unlikely (consider the motivations of a person attempting to intercept research data over the internet vs. papers stored in an office vs. credit card information). However, should interception of encrypted data occur, that data could not be decoded without the unique encryption key that is held.

Once research data is stored on a Qualtrics server, it is held in an isolated database that can only be accessed by a researcher with the correct username and password. Qualtrics employees do NOT examine customer data unless requested to do so by the account owner; additionally,

those employees are trained in the ethics of research involving human subjects. Servers are housed in a secure data facility and are monitored 24 hours-per-day and 7 days-per-week by network operations personnel for all aspects of operational security. Biometric/intrusion sensors, card readers, personal identification numbers, and environmental sensors are used to ensure server integrity and safety. Redundant HVAC systems ensure an optimized operational environment. Server power is provided by a redundant, multi-stage, uninterruptible system. Even in the event of a catastrophic commercial power failure, diesel generators seamlessly provide backup power. A redundant, high-bandwidth, private transport network provides connectivity between our servers and the world. The local fiber connectivity is redundant with three fiber rings with dual entry points from Optical Carrier-12 (OC-12) hardware. This network has demonstrated 99.999% availability, which means that the network will be down no more than 5 minutes in one year. Qualtrics allows you to link two surveys together. Therefore, identifying information about participants and research data can be collected, stored, and accessed separately. If you need to collect identifying information at the same time you are collecting anonymous research data this method is, by far, the safest.

9.1.3 Access to Data and/or Specimens

Identify who will have access to the data and/or specimens. This information should not conflict with information provided in section 9.1.1.1 regarding who has access to identifiable information, if applicable.

Only [name], [name], and trained study team members (i.e., research assistants) included on this IRB protocol will have access to data on the encrypted PSU Box folders.

9.1.4 Transferring Data and/or Specimens

If the data and/or specimens will be transferred to and/or from outside collaborators, identify the collaborator to whom the data and/or specimens will be transferred and how the data and/or specimens will be transferred. This information should not conflict with information provided in section 9.1.1.1 regarding who has access to identifiable information, if applicable.

Not Applicable.

9.2 Subject Privacy

This section must address subject privacy and NOT data confidentiality.

Indicate how the research team is permitted to access any sources of information about the participants.

Describe the steps that will be taken to protect participants' privacy interests. "Privacy interest" refers to a person's desire to place limits on whom they interact with or to whom they provide personal information.

Describe what steps you will take to make the participants feel at ease with the research situation in terms of the questions being asked and the procedures being performed. "At ease" does not refer to physical discomfort, but the sense of intrusiveness a subject might experience in response to questions, examinations, and procedures.

All investigators will be asked to be aware of participant comfort and participants will be encouraged to ask questions or state concerns regarding privacy. Both prescreening measures and study procedures are designed to (and will be implemented in such a way that) preserves participant privacy. Phone calls and experimental sessions will take place in private rooms in the Moore building where participants can be

assured that the privacy of their information will not be compromised. Overall, participants will be able to address privacy concerns or questions at any time throughout the study by emailing or calling [name] at [contact].

10.0 Data and Safety Monitoring Plan

This section is required when research involves more than Minimal Risk to participants. As defined in "SOP: Definitions (HRP-001)", available in the Library in CATS IRB (<http://irb.psu.edu>), Minimal Risk is defined as the probability and magnitude of harm or discomfort anticipated in the research that are not greater in and of themselves than those ordinarily encountered in daily life or during the performance of routine physical or psychological examinations or tests. For research involving prisoners, Minimal Risk is the probability and magnitude of physical or psychological harm that is normally encountered in the daily lives, or in the routine medical, dental, or psychological examination of healthy persons. **Please complete the sections below if the research involves more than minimal risk to participants OR indicate as not applicable.**

10.1 Periodic evaluation of data

Describe the plan to periodically evaluate the data collected regarding both harms and benefits to determine whether participants remain safe.

Not Applicable.

10.2 Data that are reviewed

Describe the data that are reviewed, including safety data, untoward events, and efficacy data.

Not Applicable.

10.3 Method of collection of safety information

Describe the method by which the safety information will be collected (e.g., with case report forms, at study visits, by telephone calls and with participants).

Not Applicable.

10.4 Frequency of data collection

Describe the frequency of data collection, including when safety data collection starts.

Not Applicable.

10.5 Individuals reviewing the data

Identify the individuals who will review the data. The plan might include establishing a data and safety monitoring committee and a plan for reporting data monitoring committee findings to the IRB and the sponsor.

Not Applicable.

10.6 Frequency of review of cumulative data

Describe the frequency or periodicity of review of cumulative data.

Not Applicable.

10.7 Statistical tests

Describe the statistical tests for analyzing the safety data to determine whether harms are occurring.

Not Applicable.

10.8 Suspension of research

Describe any conditions that trigger an immediate suspension of research.

Not Applicable.

11.0 Risks

List the reasonably foreseeable risks, discomforts, hazards, or inconveniences to the participants related to the participants' participation in the research. For each potential risk, describe the probability, magnitude, duration, and reversibility. Consider all types of risk including physical, psychological, social, legal, and economic risks. If applicable, indicate which procedures may have risks to the participants that are currently unforeseeable. If applicable, indicate which procedures may have risks to an embryo or fetus should the subject be or become pregnant. If applicable, describe risks to others who are not participants.

Please keep in mind that loss of confidentiality is a potential risk when conducting human subject research and should be addressed as such.

Possible risks:

In the assessment process, it is possible that participants may experience some distress as they are reminded of difficult memories, asked to answer personal questions, and asked about past and current symptoms. In counseling, the process of therapy may increase distress over the short term, especially as the counseling provided in this study involves exposure to elicited anxiety around feared stimuli. The risks involved in the assessment and therapy procedures are no more than those involved in other therapy settings.

The responses to questions concerning illegal drug use could be self-incriminating and harmful if they became known outside the study. Precautions will be taken to ensure the safety and security of participant's personal information.

It is also possible that participants experience physical distress, including muscle tension, upset stomach, or other somatic symptoms associated with anxiety and arousal. The risks involved in the assessment and therapy procedures are no more than those involved in other therapy settings.

Due to the nature of virtual reality, there is potential for users to develop cybersickness. Cybersickness involves users feeling some dizziness, abdominal symptoms as a result of using virtual reality. However, the time within the virtual reality world in our study has been adapted (*under 40 mins per use*) to reduce eye strain and cybersickness (Bouchard, Loranger, Robillard, & Larouche, 2012). None of the participants in Bouchard and Wiederhold (2009) had to stop the immersion due to negative side effects. For 92% of the 157 adult users, the intensity of symptoms was rated as "slight".

The design of the virtual reality scripts has minimal unnecessary movement of the user within the virtual reality space, which is a high predictor for inducing cybersickness and, hence, limits the likelihood of users developing cybersickness.

Additionally, there is social stigma attached to individuals who have a history of mental health diagnoses. Given this, precautions will be taken to ensure the safety and security of subject's personal information.

For risks associated with mental health or physical discomfort the following precautions will be taken:

- Participants will be informed of these risks in advance.
- As part of treatment, participants will gain coping skills to better manage the distressing symptoms.
- Treatment and assessments will be provided by doctoral students who have training in mental health treatment, and who can provide support to research participants.
- Research therapists involved in the study will be supervised by a licensed psychologist or advanced graduate student therapist who can provide additional oversight and resources to either the research therapist or participant to ensure participants are getting appropriate treatment.
- Each treatment session will be under 40 mins to minimize the likelihood of a user developing cybersickness.
- Unwanted side effects of cybersickness are monitored using a well-established instrument (Simulator Sickness Questionnaire [SSQ]; Kennedy, Lane, Berbaum, & Lilienthal, 1993). If a user reports significant cybersickness, research therapist will problem solve with the user. If continuous cybersickness is reported, the user may not be a good fit for the intervention.

For risks related to disclosure of information outside of the study, the following precautions will be taken:

- Participants will be informed of these risks in advance.
- All necessary steps, as dictated by law and the American Psychological Association ethics code will be followed to ensure the safety of participant's data.
- Only individuals who are directly involved with the research project will have access to the research information.

Why this study is of minimal risk:

Participants involved in this study will be asked to discuss difficult topics including current symptoms, past trauma, substance use, and psychiatric history. Despite the discomfort this may cause, this risk remains minimal as the procedures involved in the study are similar to those that individuals would encounter when engaging in any other mental health treatment.

Circumstances under which the study will be ended to prevent future risk:

The study will be ended if the protocol is shown to cause unnecessary harm to participants without any compensatory benefit. The Beck Anxiety Inventory (BAI; Beck & Steer, 1993) will be used to assess changes in symptoms every week. If no response, or negative response, (as operationalized as a 15% increase in severity on BAI scores for two consecutive sessions after initial adjustment to treatment has been made) continues for at least 5 participants, or if at least 5 participants are referred out due to requiring more care, the study will be stopped. This figure was chosen as controlled studies of single-diagnosis treatment trials often show that 5-10% of the study populations may exhibit an increase in symptoms while participating in a therapy study and 35- 40% report little benefit (Hansen, Lambert, & Forman, 2002). Given that the community population served by this study may be more complex than the populations seen in clinical trials the number was slightly increased.

It is expected that some participants will see a temporary increase in symptoms over the course of treatment due to the need to discuss difficult emotional information in treatment. To help ensure that any of the participant's concerns are addressed and that the treatment offered is responsive to the participant's needs, ongoing symptom monitoring will assist with the identification of individuals who do not appear to be benefiting from treatment and adverse effects will also be monitored through the assessment process (i.e., through the use of the Negative Effects Questionnaire; Rozental, Kottorp, Boettcher, Andersson, & Carlbring, 2016). This monitoring will also allow for a collaborative discussion with study participants so that adjustments can be made in their treatment as needed. If an individual participant becomes an imminent risk to themselves or others, their participation in the study will end and they will be referred to an appropriate level of care. We will ask such

participants to contact the Centre County Community Care Behavioral Health Organization at 1 [contact] to uncover other appropriate behavioral health treatment services they can access.

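### The study-stopping count of 5 participants does not follow from the 5-10% background rate given as its reason

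*Combined protocol and SAP*

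**What the plan says.** Section 11.0, under the circumstances for ending the study, opens with a principle: "The study will be ended if the protocol is shown to cause unnecessary harm to participants without any compensatory benefit". It then sets two triggers, which apply if the pattern "continues for at least 5 participants, or if at least 5 participants are referred out".

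- Worsening: "If no response, or negative response, (as operationalized as a 15% increase in severity on BAI scores for two consecutive sessions", counted only after an initial adjustment to treatment, and only if it continues in at least 5 participants.
- Referral: "if at least 5 participants are referred out due to requiring more care, the study will be stopped".

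The reason given for the figure is that in controlled treatment trials "5-10% of the study populations may exhibit an increase in symptoms while participating in a therapy study" and "35- 40% report little benefit". Because this population may be more complex, "the number was slightly increased". The same section adds: "It is expected that some participants will see a temporary increase in symptoms over the course of treatment".

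Section 8.1 plans 750 participants. Section 8.2 splits them into 300 and 300 in the two active arms and 150 on the waitlist. Under Section 7.2, waitlist participants are offered the same treatment after 8 weeks, and between-session symptom assessment applies to them once treatment starts. Up to 750 people can therefore contribute events.

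**The concern.** The rationale describes a threshold set a little above the worsening expected in any therapy trial. A threshold of that kind is a proportion, or a count tied to a known number treated. The protocol gives a bare count for a study of 750, with no denominator, time window or review schedule. As written, the count accumulates over the whole study.

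If the counted event occurs at anything like the background rate, a mandatory stop would follow without any sign of harm above background, which is not the test the paragraph opens with. If the event is much rarer, the rule may never fire. The protocol does not let a reader tell which.

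Two definitions are also incomplete. The 15% rise has no stated reference score (baseline, previous session or another). Non-response is named in the trigger, but the only operational definition describes a rise in BAI.

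**Working it through.** **Inputs.** Trigger count 5, background worsening 5-10% and little benefit 35-40% (Section 11.0); total 750 (Section 8.1); active arms 300 + 300 = 600 (Section 8.2); 75 participants per semester (Section 16.3).

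**Step 1. Can the figure of 5 be reproduced from its rationale?** The section gives no formula, so I tried each available denominator.

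- All treated: 5/750 = 0.67%.
- Active arms: 5/600 = 0.83%.
- Denominator at which 5 equals the cited rate: 5/0.10 = 50 and 5/0.05 = 100.
- One semester: 5/75 = 6.7%. This would fit a slight increase over 5%, but nothing in the text makes the rule per semester.

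At 5-10% the expected number is 37.5 to 75 of 750, or 30 to 60 of 600. The count of 5 is not reproduced for the planned sample.

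**Step 2. Chance that the worsening trigger fires.** Let X be the number of participants with the event among N treated, with independent outcomes and a common rate p. Then P(stop) = P(X ≥ 5) = 1 − Σ C(N,x) pˣ (1−p)ᴺ⁻ˣ, summed over x = 0 to 4. The documents give no p for this event, so p is an assumption shown over a range.

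| Assumed rate p | N = 750 | N = 600 |
|---|---|---|
| 0.2% | 2% | 1% |
| 0.5% | 32% | 18% |
| 1% | 87% | 72% |
| 2% | 99.9% | 99.3% |
| 5% or 10% | almost certain | almost certain |

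The rule is more likely than not to fire once p exceeds 0.62% (N = 750) or 0.78% (N = 600). The chance stays at or below 5% only if p is at most about 0.26% or 0.33%, respectively.

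**Step 3. When it would fire if the event did occur at the cited rate.** The median number treated at the fifth case is the smallest n with P(X ≥ 5) of at least 0.5. That is 94 at 5% and 47 at 10%. At 75 per semester, these fall in the second and first semester.

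**The case against.** The strongest objection is that the 5-10% and the trigger describe different events. The cited rate covers any increase in symptoms. The trigger needs a 15% BAI rise on two consecutive sessions, after an initial adjustment, and continuing. Those conditions are there to filter out the temporary increases the protocol expects. This stands, and it limits what can be concluded. A reader might infer that the threshold is 6 to 15 times too low, or that the study is bound to stop early. The documents support neither, because they give no rate for the stricter event.

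A second objection is that a low fixed count is simply cautious. A sponsor and IRB may choose that, but this protocol claims something else: a figure derived from background rates and then raised.

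Three other stronger readings also fail.

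- If non-response counted at 35-40%, the median stop would come at 14 or 12 treated. That needs a criterion the text does not contain, and it equates reporting little benefit with non-response. The workable reading is that only the BAI rise counts, so this is a point to clarify.
- The referral trigger might seem to conflict with Section 3.3.1, where needing more intensive care is a reason for individual withdrawal. One rule removes a person and the other counts such cases across the study, so both can apply.
- Section 10 being marked not applicable might look like a gap. The template requires that section only above minimal risk, and Section 11.0 argues that the study is of minimal risk.

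**Conclusion.** The stopping threshold is wrong as written, because it does not follow from the reason given for it. Five is 0.67% of 750 or 0.83% of 600, and it corresponds to 5-10% only for 50 to 100 participants. This finding needs no assumption about event rates.

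The practical consequence does depend on an unknown rate. Between 0.2% and 2%, the chance of stopping on this trigger runs from 2% to 99.9% at N = 750 and from 1% to 99.3% at N = 600, assuming independent outcomes and that all N are treated. Only if the strict event occurred at the cited 5-10% would stopping be almost certain, and then with nothing above background shown.

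The missing reference score and the undefined status of non-response are clarifications. The point should be fixed, but it is not of the highest severity: the rule governs whether the trial continues, and no bias in the efficacy estimate has been shown.

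**What to change.** Restate the worsening trigger as a proportion of participants treated so far, set above the cited background as the text intends. Give the minimum number treated, the review schedule, and the probability of triggering at background and elevated rates. Keep early protection, for example by reviewing each worsening case individually until the minimum is reached.

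State the reference score for the 15% BAI rise. State that non-response leads to individual treatment adjustment and does not count towards stopping, unless it is given its own criterion and a threshold above 35-40%. The referral trigger may stay a count if the sponsor and IRB prefer, with its denominator stated.

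As an illustration only: review after every 50 treated, and stop if the posterior probability (flat prior) that the rate exceeds 10% is at least 0.90. This means 8 of 50, 14 of 100 or 26 of 200. Over 600 to 750 treated it triggers 0.3% of the time at a true rate of 5%, 34-36% at 10% and over 99% at 15%. At 15% the median stop is at 100 treated with about 14 worsened. The sponsor and IRB should set the values.

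The cost is protocol wording, a short table of triggering probabilities and IRB re-review; the BAI is already collected weekly. At larger numbers treated, more participants may worsen before a stop than under a fixed count of 5. A proportion is not always the looser rule: one that stops above 10% once at least 20 are treated fires at 3 of 20.
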